6.10 Date of last contact

The date of last contact is derived for patients not known to have died at the analysis cut-off date (see section 7.4) based on the latest date among the following:

- Actual assessment dates (Labs, vital signs, performance status, tumour imaging, EOT completion, PK sample collection dates).
- Antineoplastic therapies administered after study drug discontinuation.
- Adverse events dates.
- “Date of contact” or “Last known date patient alive” collected on the “Survival Follow-up” eCRF page (if applicable).
- Date of study completion or discontinuation from the “End of Survival Follow-up” eCRF page.
- Study treatment start/end date.

The date of last contact is defined as the latest date from the above list or the cut-off date whichever comes first. In case that a date is only partially complete the following rules will be applied. If month and year are present and only the day is missing the first day of the month will be used to impute the missing date. If day and month or year is missing the date will not be imputed. The date of last contact is used for censoring of patients in the analysis of overall survival and time to next treatment.

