7.2.5 Survival Follow-up

After Safety Follow-up Visit, a phone call will be made to the patient (or the patient's family) every 90 days (+ 2 weeks) for to cover a duration of up to 5 years from Cycle 1 Day 1 to inquire about the patient's status, second primary malignancy (SPM) and information on any antineoplastic therapies utilised since discontinuation of study treatment. For patients who are lost to follow-up, at least three attempts of contact by the site should be made and documented in the source data.

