10.6.2.2 Duration of Response (DoR) and Time to Next Treatment (TTNT)

DoR is defined as the time interval between the initial time point of tumour response (CR or PR whichever status is recorded first) and the first date that recurrence of progressive disease is documented. Response duration by the local and central assessment will be tabulated with descriptive statistics.

Disease progression is defined as the first occurrence of progressive disease according to the revised response criteria ([Cheson et al., 2007](#)) as assessed by central radiology / clinical readers.

TTNT is defined as the time from study entry (= first dosing) to the institution of next therapy for any reason including disease progression, treatment toxicity and patient preference. TTNT will be descriptively analysed.

10.6.2.3 Time to Event Variables: Progression-Free Survival (PFS), Overall Survival (OS), and Time to Progression (TTP)

PFS is defined as the time elapsed between study entry (= first dosing) and lymphoma progression or death from any cause, whichever occurs first. Patients not experiencing a lymphoma progression or death from any cause will be censored at the last available tumour assessment. The same holds true for patients who are lost-to-follow-up.

OS is defined as time from study entry (= first dosing) until the date of death from any cause. Patients who are alive but have dropped out early will be censored at the time of the last available study visit assessment.

TTP is defined as the time from study entry (= first dosing) until documented lymphoma progression or death as a result of lymphoma. The events of interest are only disease progression and death from lymphoma. Death from other causes will not be taken into account (will be censored) in the TTP evaluation. Patients not experiencing progressive disease will be censored at the last NHL assessment. Deaths from other causes will be censored at the time of death. Early drop-outs without any documented date of progression will be censored at the time of the last NHL assessment.

Kaplan-Meier methodology will be used to evaluate median survival, presenting corresponding statistical parameters and Kaplan-Meier survival curves. Further analyses concerning influence of IPI and GC/non-GC B-cells will be specified in the SAP.

TTP will be compared to the TTP of the patients' most recent therapy by tabulating descriptive statistics (including 95% confidence limits).

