6.9 Start and end date for time to event variables

Assessment date

For each assessment (i.e. evaluation number), the **assessment date** is calculated as the latest of all measurement dates (e.g. X-ray, CT-scan) if the overall response at that assessment is CR/PR/SD/UNK/NE.

Otherwise - if overall response is progression – the assessment date is calculated as the earliest date of all measurement dates at that evaluation number.

Start dates

For all “time to event” variables, other than duration of response, the start date of study treatment will be used as the start date.

For the calculation of duration of response the following start date should be used:

Date of first documented response is the assessment date of the first overall response of CR or PR.

End dates

The end dates which are used to calculate ‘time to event’ variables are defined as follows:

- Date of death (during treatment as recorded on the treatment completion page or during follow-up as recorded on the study evaluation completion page or the survival follow-up page).
- Date of progression is the first assessment date at which the overall response was recorded as progressive disease.
- When there is no documentation of radiologic evidence of progression, and the patient discontinued for ‘Disease progression’ due to documented clinical deterioration of disease, the date of discontinuation is used as date of progression.
- If no post-baseline assessments are available (before an event or a censoring reason occurred) the start date of study treatment is used as the end date.

Calculation of ‘time to event’ variables

Time to event = End Date - Start date + 1 (in days).

When no post-baseline tumor assessments are available, the start date of study treatment will be used as end date (duration = 1 day).

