6.13.9 Withdrawal of informed consent

Any data collected in the clinical database after a patient withdraws informed consent from all further participation in the trial, will not be included in the analysis data sets. The date on which a patient withdraws full consent is recorded in the eCRF (on the end of treatment eCRF page). Note: Patients who withdraw consent from treatment but consent to post-treatment follow up and/or survival follow up are not considered as having withdrawn full consent and no such withdrawal of consent date is recorded in the eCRF. Such post-treatment assessments will be included in the analysis data sets.

Any data that is entered in the clinical database without the consent of the patient will be excluded from the analysis sets. Only exceptions are the information entered to close a page after the date of withdrawal of consent e.g. End of Treatment, End of post-treatment follow-up.

For OS, death events in some countries can be reported if the death event can be confirmed to be captured from public records. If confirmed, the events will be included in the analysis data sets.

Third party data, e.g. PK, biomarker etc., collected in the clinical database without having obtained consent for collection will not be included in the analysis data sets. Data from such samples if collected prior to the date of consent withdrawal will be included in the analysis unless specific request is made by the patient not to analyze the sample. These data will be excluded by the presence of the appropriate protocol deviation criterion.

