10.4.3 Censoring rules and imputation

Patients who are alive or who drop out early for any reason will be censored at date of last contact.

If for a patient's death month and year are provided but the day is missing, the day will set to the first day of the month, unless other qualifying study data support survival until a later date during the same month. If day and month or year is missing, no imputation will be done and the date of death will be censored at the date of last contact. A listing showing the information on eCRF pages for survival follow-up and end of survival follow-up will be presented (for the SAF).

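### The last-contact date that censors OS and TTNT can be a study-discontinuation date on which the patient was not contacted, which would bias survival slightly upward for patients lost to follow-up

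*SAP*

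**What the plan says.** SAP 6.10 derives last contact "based on the latest date among the following" and caps it at the data cut-off. The list holds actual assessment dates, later antineoplastic therapies, adverse event dates, study treatment dates, and two items from the survival pages. The first of these is the contact date or "Last known date patient alive" on the Survival Follow-up page. The second is the "Date of study completion or discontinuation from the" End of Survival Follow-up page. Nothing limits the second item to patients who were spoken to on that date.

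The derived date is used in these places:

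- **OS (SAP 10.4.3):** "Patients who are alive or who drop out early for any reason will be censored at date of last contact".
- **TTNT (SAP 10.6.2):** patients with no documented new therapy are censored at the same date.
- **Follow-up (SAP 8.3.2 and 10.4.4):** the follow-up summary reuses the OS event or censoring date, and median OS follow-up by reverse Kaplan-Meier is built on it.

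The protocol words OS censoring differently in 10.6.2.3: "Patients who are alive but have dropped out early will be censored at the time of the last available study visit assessment". Protocol 5.3.1 and 7.2.5 provide for phone contact every 90 days after the safety visit. For lost patients, 7.2.5 adds that "at least three attempts of contact by the site should be made and documented in the source data". It does not say how far apart the attempts should be.

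**The concern.** A censoring date should be the last time the patient was known to be free of the event and would have been counted if the event had occurred. The date a site closes a lost patient's survival page need not meet that test. It is normally set after contact has failed, and any death since the last successful call is unknown to the site. Because SAP 6.10 takes the latest date, such an entry displaces direct evidence of life from the same list.

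The error runs one way. The lost patient adds person-time and cannot add an event, so OS and TTNT are biased upward. The reported follow-up, which SAP 8.3.2 offers as a description of data maturity, is lengthened by the same patients whose follow-up failed. No planned analysis changes the OS censoring date: SAP 10.4.5 repeats OS on the PPS and 20.8.1 on the SAF, and both change only the population. OS probabilities are planned out to 48 months (SAP 10.4.4 and Addendum 8.0), where losses have had time to accumulate.

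**Working it through.** The plan states no event count, rate or power for OS or TTNT, so there is no figure of its own to reproduce. The size of the effect was therefore worked out under stated assumptions.

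**Inputs from the documents**

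- About 80 patients (SAP 5.3).
- A 10% drop-out rate (SAP 5.3). It was set for the ORR sample size and is only a guide to loss from survival follow-up.
- Primary analysis about 12 months after the last enrolment (SAP 5.4.2).
- Calls every 90 days (Protocol 5.3.1).
- Median OS of 10.7 months in a cited lenalidomide plus rituximab study (Protocol 1.3.3), used as one scenario.

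**Assumptions not in the documents**

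- Exponential OS with median M of 10.7 or 24 months.
- Exponential loss, independent of death, at a rate giving a proportion q lost by 24 months in the absence of death.
- Uniform accrual over 18 months.
- A gap g between last known alive and the recorded date of 3 months (one call cycle) or 9 months (three cycles).
- Deaths in the gap unknown to the site.

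**Closed form.** Let λ = ln 2 / M and μ = −ln(1 − q) / 24 per month. From time g onward, the ratio of lost-but-retained patients to patients truly under observation is

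r = [μ / (λ + μ)] × (e^((λ + μ)g) − 1),

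and the apparent hazard is λ / (1 + r). Before time g, replace g by t. Cut-off removes both kinds of patient alike, so r is unaffected.

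For M = 24 and q = 10%: λ = 0.02888 and μ = 0.00439.

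- **g = 3:** r = 0.0139, so the hazard after month 3 is 0.028487. Cumulative hazard to 24 months = 0.0861 (months 0 to 3) + 21 × 0.028487 = 0.6843. Survival = e^(−0.6843) = 0.5045 against a true 0.5000, a bias of +0.45 points.
- **g = 9:** r = 0.0461, so the hazard after month 9 is 0.027609. Cumulative hazard = 0.2544 + 15 × 0.027609 = 0.6685. Survival = 0.5125, a bias of +1.25 points.

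**Simulation.** The table gives the mean difference between the SAP rule and censoring at last known alive, from 1,500 trials of 80 patients per scenario.

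| Median OS (months) | Lost by 24 months | Gap (months) | Bias at 12 months (points) | Bias at 24 months (points) |
|---|---|---|---|---|
| 10.7 | 10% | 3 | +0.5 | +0.5 |
| 10.7 | 10% | 9 | +1.1 | +1.4 |
| 24 | 10% | 3 | +0.3 | +0.4 |
| 24 | 10% | 9 | +0.7 | +1.3 |
| 10.7 | 30% | 3 | +1.5 | +1.5 |
| 10.7 | 30% | 9 | +3.6 | +4.8 |
| 24 | 30% | 3 | +1.0 | +1.5 |
| 24 | 30% | 9 | +2.2 | +4.2 |

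The 10%, median-24 rows agree with the closed form. In those runs the share of patients actually lost was 6.6%, about 5 of 80, because the others died or reached cut-off first. Censoring at last known alive recovered the true curve closely in every scenario. In the worst case (30% lost, 9-month gap) the estimated median moved from 10.8 to 11.8 months, or from 24.1 to 27.9. With g = 0 the bias is zero.

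TTNT was not simulated. The mechanism is the same, but its size is not given here.

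**The case against.** The best defence is that the delay is inferred. The eCRF field is not defined in the documents. A site may enter the date of last contact there, and then nothing is lost. For completers, and usually for patients who withdraw consent, the date reflects real contact, so only lost patients can be affected. All of this stands, and it makes the bias conditional.

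A reader might infer from the 90-day calls and the three attempts that lost patients are carried for nine months. The protocol does not say so: 90 days is the routine call interval, and three attempts could fall within a week. Nine months is an upper scenario. About three months is the more natural reading if the field holds the date declared lost.

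The effect is also small against sampling error. At 50% survival with 80 patients the standard error is √(0.5 × 0.5 / 80) = 5.6 points even without censoring, a 95% half-width of 11 points. OS is secondary and no formal test is planned. Losses would be partly visible, because SAP 8.3.1 tabulates reasons for leaving survival follow-up and 10.4.3 lists both survival pages. But a reader would have to re-derive the curve to see the effect on OS.

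The protocol conflict should not be pressed too far. Survival follow-up is by phone, so a literal study-visit rule would discard successful calls. The SAP is right to go beyond it, but it should say so and stop at evidence of life.

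Two neighbouring rules invite stronger readings than the text supports:

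- **SAP 6.9.** Its closing sentence sets duration to one day when there is no post-baseline scan, and makes no exception. Someone might infer that such deaths would be placed at Day 1 for OS. The endpoint rules override this: Table 13 uses the date of death for PFS, and 10.4.2 and 10.4.3 define OS by death or last contact. It is loose wording.
- **SAP 6.13.9.** It states: "For OS, death events in some countries can be reported if the death event can be confirmed to be captured from public records". One might infer that patients found alive in the same records are censored before withdrawal. That is only implied. 6.13.9 is silent on them, and 7.4 also excepts some patient-status entries made after withdrawal. The asymmetry is a gap to close, not an established bias.

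**Conclusion.** The defect in the rule is certain: SAP 6.10 lets a date without documented contact override the last date the patient was known alive, for both OS and TTNT. If it acts, it acts upward. Whether it acts depends on what sites enter in an undefined field.

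If they enter the date declared lost, then at 10% loss the OS bias is 0.3 to 0.5 points for a 3-month gap and 0.7 to 1.4 points for a 9-month gap. It approaches 5 points only with heavy loss and a long gap. These figures rest on exponential survival, loss independent of death, and loss rates and gaps that the documents do not give.

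A flat statement that survival is overstated would go too far, because the documents cannot show that the field differs from true contact. ORR and PFS do not use this date. The change is worth making because it removes a one-directional error at almost no cost, and it leaves results unchanged if the field already records real contact.

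**What to change.** 1. In SAP 6.10, define last contact for patients not known to have died as the latest date with positive evidence of life: a dated assessment or dose, a successful contact, or the recorded last-known-alive date. Use the completion or discontinuation date only when contact on that day is documented. Apply this to OS, TTNT and both follow-up summaries.
2. Reconcile the rule with Protocol 10.6.2.3, stating that successful survival calls count as well as visits.
3. After withdrawal of consent, treat registry findings alike: either censor everyone at withdrawal, or use the registry check date for patients found alive as well as the death date for those found dead.
4. State that the Day 1 fallback in SAP 6.9 applies only to censored patients in imaging-based endpoints.

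The cost is a few sentences of SAP text and one revised derived date. OS, TTNT and reported follow-up may become slightly less favourable. If the main rule cannot be changed, the minimum is an OS and TTNT sensitivity analysis censored at last known alive.

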6.11 Analysis windows

For parameters that will be summarized by visit, the nominal visit as recorded in the eCRF will be used. There will be no additional analysis windowing done based on the assessment date.

In order to summarize over time, parameters recorded at each visit (i.e. performance status, PK, vital signs), assessments (including unscheduled ones) will be time-slotted if indicated.

6.12 Selection of data in the event of multiple records in a window

Depending on the statistical analysis method, single values may be required for each analysis window. For example, change from baseline by visit usually requires a single value per visit, whereas a time-to-event analysis would not require one value per analysis window but rather one value for the study.

Unless otherwise noted throughout the rest of this document, when a single value is needed, the following rule(s) will be used:

-
- If more than one assessment occurs during the same nominal visit time window of the planned visit, select the record closest to the nominal day for that particular visit day.
 - If there are two assessments that are equidistant from the nominal planned visit day, the data of the assessment after the scheduled study day will be used.
 - The last measurement will be used if multiple measurements are all taken on the same day.

6.13 Analysis populations

The following analysis populations will be defined:

6.13.1 All patients screened

The All patients screened population consists of all patients who signed informed consent and completed the *Informed Consent* eCRF page.

6.13.2 Enrolled patients

The Enrolled patients population consists of all patients who received at least one dose of any study drug (MOR00208 or LEN).

6.13.3 Full analysis set (FAS)

The FAS includes all patients who received at least one dose of MOR00208 and one dose of LEN. This means that both study drugs must have been administered at least once. The FAS will be the primary population for the analysis of efficacy and baseline characteristics.

A listing showing the patients who have been excluded from the efficacy analysis will be provided.

6.13.4 Per protocol set (PPS)

The PPS includes all patients in the FAS who do not have any major protocol deviations that could confound the interpretation of the primary analyses conducted on the FAS. The PPS includes all patients in the FAS who have received at least one dose of MOR00208 and LEN, and underwent at least one post-baseline response assessment.

Those protocol deviations leading to exclusion from the PPS will be listed including the patient number

STATISTICAL ANALYSIS PLAN

 MorphoSys AG
 MOR208C203

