10 STATISTICAL METHODS AND PLANNED ANALYSIS

10.1 Populations for Analysis

The following analysis populations will be used:

- **Full analysis set (FAS):**
The FAS includes all patients who received at least one dose of MOR00208 and one dose of LEN. This means that both study drugs must have been applied at least once.
- **Per protocol set (PPS):**
The PPS is the subset of all subjects in the FAS without any major protocol non-compliances. All patients in the FAS, had at least one dose of MOR00208 and one dose of LEN drug. Patients without any post-baseline assessment of DLBCL response or having major protocol deviations will be excluded from the PPS.
- **Safety analysis set (SAF):**
All patients who received at least one dose of MOR00208 or LEN study drug.

Primary, secondary and supportive efficacy parameters will be evaluated using the FAS and PPS, while safety parameter evaluations will use the safety set (SAF), as well as for evaluations on immunogenicity and biomarkers.

The primary analysis of the primary efficacy endpoint will be based on the FAS, whereas the analysis using the PPS has a supportive function. Decisions about whether a protocol deviation is relevant for the exclusion of a patient from the PPS will be made before database closure.

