10.2.5 Main analysis

- The tumour assessments will be derived according to the IWG treatment response criteria for malignant lymphoma (Cheson et al., 2007), by an Independent Radiology/Clinical Review Committee (IRC). The review process will be defined in the IRC Charter.
- The distribution of PFS will be estimated using the Kaplan-Meier (K-M) method. The median PFS time along with 95% confidence intervals will be presented (Brookmeyer and Crowley 1982). 25th and 75th percentiles will be considered as well.
- The PFS probabilities at specific time points (1 month, 3 months, 6 months, 12 months, 18 months, 24 months, 30 months), and the associated 95% CIs (Greenwood formula) will be summarized.
- PFS events will be described according to the type of event (death, documented tumour progression).
- The reason for censoring will be tabulated.
- A plot of the Kaplan-Meier curve for PFS will be provided.
- The median follow-up time for PFS including a 95% confidence interval (Brookmeyer and Crowley 1982) will be calculated using the reverse Kaplan-Meier method.
- No formal hypothesis testing will be conducted.
- The main analysis will be conducted on the FAS for both the IRC and INV response assessment.

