10.2.6 Sensitivity analyses

- The main analysis as described in Section 10.2.5 will be conducted on the PPS.
- The main analysis as described in Section 10.2.5 will be conducted based on the INV response assessment as entered on the 'Lymphoma Tumour Assessment' eCRF page. The same censoring rules will apply as for the analysis based on the IRC assessment. If the response assessment is not based on radiological examination the date when the diagnosis of relapse or progression was made by the investigator is considered as the date of progression. The analysis will be conducted using both the FAS and the PPS.
- Patients having more than one missed visit, but having an available death date, will be included in the time-to-event analysis and considered as having a PFS event. The analysis will be performed on the FAS for both IRC and INV response assessment.

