10.4.4 Main analysis

- The distribution of OS will be estimated using the Kaplan-Meier (K-M) method. The median OS time along with 95% confidence intervals will be presented (Brookmeyer and Crowley 1982). 25th and 75th percentiles will be considered as well.
- The OS probabilities at specific time points (1 month, 3 months, 6 months, 12 months, 18 months, 24 months, 36 months, 48 months), and the associate 95% CIs (Greenwood formula) will be summarized.
- A plot of the Kaplan-Meier curve for OS will be provided.
- The median follow-up for OS will be calculated using the reverse Kaplan-Meier method.
- No formal hypothesis testing will be conducted.
- The main analysis will be conducted on the FAS.

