10.4.5 Sensitivity analyses

- The main analysis as described in Section 10.4.4 will be conducted on the PPS.

10.5 Secondary objective 5 and secondary objective 11

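### The PPS reruns of PFS, OS, TTP and TTNT drop patients who die before any post-baseline scan, so they probably lean upward and cannot test robustness to early deaths

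*SAP*

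**What the plan says.** SAP 6.13.4 builds the PPS from the FAS with two filters. Patients must "do not have any major protocol deviations that could confound the interpretation of the primary analyses conducted on the FAS", and they must have "underwent at least one post-baseline response assessment". Protocol 10.1 states both filters as exclusions: "Patients without any post-baseline assessment of DLBCL response or having major protocol deviations will be excluded from the PPS".

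The FAS is the main set. For PFS, SAP 10.2.5 says "The main analysis will be conducted on the FAS for both the IRC and INV response assessment"; for OS, SAP 10.4.4 says "The main analysis will be conducted on the FAS". Both are then repeated. SAP 10.2.6 lists "The main analysis as described in Section 10.2.5 will be conducted on the PPS", and the only entry in SAP 10.4.5 is "The main analysis as described in Section 10.4.4 will be conducted on the PPS". Table 2 (SAP 6.13.8) also marks TTP and TTNT for the PPS.

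All four clocks start at the first administration of any study drug (SAP 10.2.2, 10.4.2, 10.5.2, 10.6.2). The first scheduled on-treatment scan is at Cycle 3 Day 1 (SAP Table 12).

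**The concern.** A per protocol set should ask whether the result changes when patients who departed from the protocol are set aside. Having a post-baseline scan is not a matter of adherence. Someone who follows every instruction and dies on day 40 unscanned is excluded, although that death counts as an OS event on the FAS, and as a PFS event under Table 13. Patients who remain in the PPS are, by construction, alive until they have had a scan, yet their time is counted from first dose.

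OS needs no scan at all, and the PPS run is the one sensitivity analysis that SAP 10.4.5 offers for it. A reader who sees FAS and PPS agree, or the PPS come out slightly better, may take that as confirmation. On early deaths it confirms nothing, because those deaths have been taken out.

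The SAP handles a similar condition differently elsewhere. The safety set also requires a post-baseline assessment, but SAP 6.13.5 counts death as one. The PPS has no such provision.

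**Working it through.** **Inputs.** The documents give no number or expected share of patients without a post-baseline assessment, so there is no plan figure to reproduce for the effect itself. Two dates follow from the schedule: Cycle 3 Day 1 is study day 2 × 28 + 1 = 57, and Table 14 allows 4 × 28 + 2 = 114 days from Cycle 1 Day 1 before an event with no scan is censored.

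**What an unscanned patient contributes on the FAS**
- PFS: a death within the 114-day window is an event at the date of death (Table 13). A later death with no scan is censored back to Cycle 1 Day 1. A patient with no event ends at day 1 (SAP 6.9). Removing either of the last two groups leaves the Kaplan-Meier curve unchanged, so the no-scan filter taken alone can raise PFS but not lower it.
- OS: every death is an event. A living patient is censored at last contact (SAP 10.4.3), and patients who stop treatment are still telephoned every 90 days (Protocol 5.3.1). Removing unscanned patients can therefore take out survivors as well as deaths.

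**General relation.** With no censoring before time t, let e be the share of the FAS removed and R(t) the fraction of the removed patients still event-free at t. Then

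S_PPS(t) = [S_FAS(t) − e·R(t)] / (1 − e).

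The PPS is higher only if R(t) is below S_FAS(t). If every removed patient is an unscanned early death, R = 0 and S_PPS = S_FAS/(1 − e). For an assumed 12-month OS of 70%: 0.70/0.95 = 73.7% at e = 5%, and 0.70/0.90 = 77.8% at e = 10%.

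**Illustration with 80 patients.** This is an assumption, not a forecast. Times after day 57 are exponential with medians of 3.7 months (PFS) and 10.7 months (OS), borrowed from the lenalidomide plus rituximab study cited in Protocol 1.3.3. A median OS of 10.7 months implies 1 − 2^(−57/30.4375/10.7) = 11.4% dead by day 57, about 9 of 80. The range taken for unscanned deaths is 2 to 9.

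| Removed from the 80 | Measure | FAS | PPS |
|---|---|---|---|
| 2 unscanned deaths | 12-month OS | 40/80 = 50.0% | 40/78 = 51.3% |
| 9 unscanned deaths | 12-month OS | 37/80 = 46.25% | 37/71 = 52.1% |
| 2 unscanned deaths | 12-month PFS | 12/80 = 15.0% | 12/78 = 15.4% |
| 9 unscanned deaths | 12-month PFS | 11/80 = 13.75% | 11/71 = 15.5% |
| 2 unscanned deaths, 4 unscanned but alive | 12-month OS | 42/80 = 52.5% | 38/74 = 51.4% |
| 4 unscanned deaths, 1 major deviator event-free at 24 months | 12-month PFS | 12/80 = 15.0% | 11/75 = 14.7% |
| 4 unscanned deaths, 6 such deviators | 12-month PFS | 16/80 = 20.0% | 10/70 = 14.3% |

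In the all-deaths cases, median OS moves from 11.99 to 12.38 months (2 deaths) and from 10.54 to 12.57 months (9 deaths). The last three rows show the opposite direction: it needs either survivors among the unscanned (OS) or major deviators who did well (either endpoint).

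**The case against.** The strongest reply is that little depends on this set. The FAS is the main population, no formal test is attached to PFS or OS, and Protocol 10.1 says of the primary endpoint that the FAS leads, "whereas the analysis using the PPS has a supportive function". Other planned analyses keep early deaths. Addendum 5.0 (SAP 20.8.1) repeats PFS and OS on the safety set. SAP 10.2.6 counts deaths after missed visits as PFS events on the FAS, and SAP 20.9 applies alternative PFS censoring rules. All of this stands, and it limits the consequence. It does not repair the PPS run, which is still presented as a sensitivity analysis.

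A reader might go further and infer that the PPS can only look better than the FAS. The documents do not support that. Major deviators also leave the PPS, and their outcomes may be better or worse than average. For OS, unscanned patients may be alive in follow-up. The last three rows of the table are counterexamples.

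A reader might also infer that every patient who dies before day 57 is lost. That is too strong as well. Protocol 7.2.14.1 provides an end-of-treatment scan for patients withdrawn early for reasons other than progression, accepts CT for those who stop within Cycle 1, and permits extra scans, so some patients qualify before Cycle 3. This same rule suggests that those who remain unscanned will include a fair share of deaths, which is why an upward lean is the likelier direction.

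**Conclusion.** The point holds in limited form. The PPS condition removes unscanned deaths from PFS, OS, TTP and TTNT. The resulting estimates are probably biased upward, and they cannot test robustness to early deaths whichever way they fall. The direction is likely, not guaranteed. The size cannot be computed from the documents. The 1/(1 − e) inflation applies only if every removed patient is an unscanned early death and no deviator is removed, and the 70% and the values of e are assumptions. No FAS result changes. For OS, the gap in SAP 10.4.5 is partly filled by the safety-set analysis in Addendum 5.0.

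**What to change.** For PFS, OS, TTP and TTNT, define the PPS by absence of major protocol deviations only, and delete the post-baseline-assessment condition in SAP 6.13.4. Because Protocol 10.1 contains the same exclusion, either amend it to match or record the departure in the SAP; changing the SAP alone would leave the two documents in conflict.

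Starting the clock at a Cycle 3 Day 1 landmark is a poorer alternative, since earlier end-of-treatment or extra scans can qualify a patient before that date. ORR needs no change for this reason: SAP 9.2 counts unassessed patients as non-responders and SAP 9.3 already reports a version without them.

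The cost is one sentence, one population flag, a line on the protocol, and supportive figures that may be slightly less favourable.
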